1.1.2. Document and Study Objectives

This statistical analysis plan (SAP) is designed to outline the methods to be used in the analysis of study data to address the study objectives of Study 008. Populations for analysis, data handling rules, statistical methods, and formats for data presentation are provided. The statistical analyses and summary tabulations described in this SAP will provide the basis for the results sections of the clinical study report (CSR) for this trial.

This SAP will also outline any differences in the currently planned analytical objectives relative to those planned in the study protocol.

1.1.2.1. Primary Objective

The primary objective of the study is to evaluate the TTR reduction of patisiran in hATTR amyloidosis patients with disease progression after OLT.

1.1.2.2. Secondary Objectives

The secondary objectives of the study are to:

- Evaluate the effect of patisiran on neuropathy.
- Evaluate the effect of patisiran on patient reported outcomes including QoL, activities of daily living and autonomic neuropathy symptoms.
- Characterize the effect on nutritional status.

1.1.2.3. Exploratory Objectives

The exploratory objectives of the study are to:

- Characterize exploratory measures of clinical activity (disease stage, functional status).
- Evaluate PK.
- Assess for anti-drug antibodies (ADA) against patisiran.

1.1.2.4. Safety Objective

The safety objective of the study is to evaluate the safety and tolerability of patisiran in hATTR amyloidosis patients with disease progression after OLT.

1.2. Study Design

1.2.1. Synopsis of Study Design

Study 008 is a global Phase 3b open-label study designed to evaluate the safety, efficacy, and PK of patisiran in patients with hATTR amyloidosis with disease progression after liver transplant. All eligible patients will be administered open-label patisiran.

The open-label design is supported by previous studies, including a pivotal Phase 3 double-blind, placebo-controlled study (ALN-TTR02-004; hereinafter referred to as the APOLLO study). The clinical benefits seen in the APOLLO study were observed in association with an 80% reduction of TTR with patisiran within 10 to 14 days after a single dose, which was maintained over the duration of the 18-month study compared to no change with placebo. The primary efficacy endpoint in the current study, TTR reduction, is an objective measurement and not susceptible to bias of clinical study center staff or study patients and therefore does not require a blinded placebo group for accurate interpretation.

Consented eligible patients enrolled in this study will receive 0.3 mg/kg patisiran IV once every 3 weeks for 12 months. Dosing is based on actual body weight. For patients weighing 100 kg or more, patisiran will be administered at a total dose of 30 mg IV once every 3 weeks. Eligibility for this study will be confirmed before administration of the first dose on Day 1.

Safety will be assessed throughout the study. Patients will return to the clinical site for safety evaluations at Week 12, Month 6, and Month 12. Patients will be continually assessed throughout the study for adverse events (AEs). Unscheduled visits for study assessments may occur if deemed necessary by the study personnel.

Efficacy assessments will be performed at baseline, 6 and 12 months.

1.2.2. Study Procedures

The schedule of assessments is presented in Table 1 of the study protocol.

1.2.3. Efficacy, Pharmacokinetic, Immunogenicity, and Safety Assessments

1.2.3.1. Efficacy Assessments

The efficacy of patisiran will be evaluated using the following assessments:

- Serum TTR assessed using enzyme linked immunosorbent assay (ELISA)
- Neurological impairment assessed using the Neuropathy Impairment Score (NIS).
- Patient reported quality of life (QoL) using the Norfolk Quality of Life –Diabetic Neuropathy (QoL-DN) questionnaire.
- Disability reported by patients using the Rasch-built Overall Disability Scale (R-ODS).
- Autonomic neuropathy symptoms assessed using the Composite Autonomic Symptom Score (COMPASS-31).
- Nutritional status using modified body mass index (mBMI).
- Changes in ambulation and disease stage will be evaluated through Polyneuropathy disability (PND) score and familial amyloidotic polyneuropathy (FAP) stage.
- Functional impairment assessed using the Karnofsky Performance Status.

1.2.3.2. Pharmacokinetic Parameters

Concentrations of plasma siRNA (ALN-18328) and 2 novel lipid excipients (DLin-MC3-DMA and PEG2000-C-DMG) will be determined to estimate individual PK parameters using noncompartmental analysis methods.

1.2.3.3. Immunogenicity Parameters

Blood samples will be assessed for anti-PEG₂₀₀₀-C-DMG antibodies.

1.2.3.4. Safety Parameters

Safety evaluations performed during the study include monitoring of adverse events (AEs), recording of concomitant medications, physical examinations (clinically significant abnormalities observed during the physical examination are recorded on the medical history or AE electronic case report form (eCRF)), measurement of vital signs, and clinical laboratory evaluations (including hematology, serum chemistry, coagulation, liver function tests, and pregnancy testing), and liver allograft status (including checking and recording immunosuppressive drug levels every 3 months).

2. PATIENT POPULATION

2.1. Population Definitions

The following patient populations will be evaluated and used for presentation and analysis of the data:

- Safety Analysis Set: All patients who received any amount of patisiran. The Safety Analysis Set will be used for the analyses of the primary efficacy and safety assessments.
- Per Protocol Analysis Set: All patients in the Safety Analysis Set who missed ≤ 2 doses of patisiran due to the COVID-19 pandemic during the study. The Per Protocol Analysis Set will be used for the analyses of secondary and exploratory efficacy assessments.
- Pharmacokinetic Analysis Set: All patients in the Safety Analysis Set who received at least one complete dose of patisiran (see Section 4.5.1) and who have provided at least one valid post-dose PK concentration value.

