4.3.1. Discontinuation of Study Drug or Declining Procedural Assessments

Reasons for discontinuation of study drug include any of the following:

- Significant violation of the protocol
- Adverse event (AE)
- Non-adherence to treatment regimen
- Pregnancy
- Lost to follow-up
- Other reason (non-AE)
- Or, study is terminated by the Sponsor

The Investigator will confer with the Sponsor or Medical Monitor before discontinuing dosing in the patient. Patients who are pregnant will be discontinued from study drug dosing immediately (see Section 6.3.5.7 for reporting and follow-up of pregnancy). A positive urine pregnancy test should be confirmed by a serum pregnancy test before discontinuing the study drug.

Patients who discontinue study drug and/or decline procedural assessments should not be automatically removed from study. In general, patients who discontinue study drug dosing for any reason will be encouraged to remain on the study to complete the remaining assessments through the 12-month efficacy visit and approximately 4 weeks after the last dose so that their experience is captured in the final analyses.

If this occurs, the Investigator is to discuss with the patient the appropriate processes for discontinuation from study drug and must discuss with the patient the options for continuation of the Schedule of Assessments (Table 1), including different options for follow-up and collection of data (eg, in person, by phone, by mail, through family or friends, or from options not involving patient contact, such as communication with other treating physicians or from review of medical records), including endpoints and AEs, and must document this decision in the patient's medical records.

If a patient discontinues dosing due to an AE, including SAEs, the event should be followed as described in Section 6.3.5. When a patient discontinues study drug dosing, the primary reason must be recorded in the appropriate section of the eCRF. Patients who discontinue study drug

and remain on study may receive treatment consistent with local standard practice for their disease per Investigator judgment, as applicable. Safety will be captured for the entire duration of study for patients who discontinue study drug.

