7.2.1. Populations to be Analyzed

The populations (analysis sets) are defined as follows:

- Safety Analysis Set: All patients who received patisiran-LNP. The Safety Analysis Set will be used for the analysis of efficacy and safety assessments.
- Pharmacokinetic Analysis Set: All patients in the Safety Analysis Set who have provided at least one valid post-dose PK concentration value.

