4.4. Efficacy Analyses

Primary efficacy analysis will be based on the Safety Analysis Set. Secondary and exploratory efficacy analyses will be based on the Per Protocol Analysis Set. Summaries will be provided for each scheduled time point. Efficacy data will be included in by-patient data listings.

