4.7.2. Impact on Efficacy Endpoints

The Per Protocol Analysis Set as defined in Section 2.1 will be used for secondary and exploratory efficacy endpoints analyses.

Secondary and exploratory efficacy assessments on or after the onset of a serious COVID-19 AE for a patient may be censored (see Section 3.9).

Summaries of missing efficacy data due to COVID-19 pandemic will be included in a missing efficacy data summary table as described in Section 3.10.

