5. CHANGES TO PLANNED ANALYSES

Modifications to planned analysis specifications from the protocol are documented below:

Section	Description	Rationale
Section 2.1	Per Protocol Analysis Set was added.	The Per Protocol Analysis Set was added to support primary analyses of estimating treatment effects of secondary and exploratory efficacy endpoints in patients who did not miss or missed less than or equal to 2 doses of patisiran due to COVID-19.
Section 4.4.1	The Hodges-Lehmann method's estimates of median TTR percent reduction and its 2-sided 95% CI were modified to standard median TTR percent reduction and its 2-sided 95% distribution-free CI, respectively.	The reason of the change is because there is no available SAS procedure in most current SAS version for one-sample Hodges-Lehmann method. Based on simulations, the estimated medians and the 2-sided 95% CIs are similar for the two methods.
Section 3.10.1 Section 4.4.2.1 Section 4.4.2.2 Section 4.4.2.4	The primary analysis for the NIS, Norfolk QOL-DN, R-ODS and mBMI efficacy endpoints was updated to use LOCF to impute missing post-baseline values.	The changes from baseline in NIS, Norfolk QOL-DN and R-ODS assessments between Months 9 and 18 and mBMI assessments between Months 3 and 18 were relatively stable in the patisiran arm of the APOLLO study. Thus, the LOCF method was adopted to account for the potential missingness (including missingness related to COVID-19) in NIS, Norfolk QOL-DN, R-ODS and mBMI efficacy endpoints during this study.
Section 4.4.2.3	The primary analysis for the COMPASS-31 efficacy endpoint was changed to MMRM.	The changes from baseline in COMPASS-31 total score showed improvement from Month 9 to Month 18 in the patisiran arm of the APOLLO study. Thus, the MMRM method was adopted to account for potential missingness (including missingness related to COVID-19) in COMPASS-31 total score, which assumes data are Missing at Random (MAR).

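### Secondary and exploratory efficacy is analysed only on a set that drops whole patients for COVID-19-missed doses; the protocol's all-treated summary should be shown beside it

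*SAP*

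**What the plan says.** Protocol 7.2.1 (repeated in the synopsis) makes no distinction between efficacy endpoints: "The Safety Analysis Set will be used for the analysis of efficacy and safety assessments". That set is everyone who received study drug.

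SAP 2.1 narrows its use: "The Safety Analysis Set will be used for the analyses of the primary efficacy and safety assessments". It adds a Per Protocol Analysis Set, defined as "All patients in the Safety Analysis Set who missed ≤ 2 doses of patisiran due to the COVID-19 pandemic during the study", and gives that set the rest of the efficacy analyses: "The Per Protocol Analysis Set will be used for the analyses of secondary and exploratory efficacy assessments". SAP 4.4 says the same: "Secondary and exploratory efficacy analyses will be based on the Per Protocol Analysis Set". SAP 4.7.2 repeats that the set "will be used for secondary and exploratory efficacy endpoints analyses".

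SAP Section 5 discloses the change and gives its purpose: "The Per Protocol Analysis Set was added to support primary analyses of estimating treatment effects of secondary and exploratory efficacy endpoints". The amendment history (SAP Section 8) repeats it. Neither place, nor any of SAP 4.4.2 to 4.4.3, names a supporting analysis of these endpoints on the Safety Analysis Set.

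**The concern.** The exclusion depends on a post-baseline event and acts on the patient, not on the affected assessments. Someone who misses three doses for COVID-19 reasons in the second half of the year loses the Month 12 result and also a Month 6 result obtained under full dosing. The SAP has narrower tools: section 3.9 allows assessments to be censored from the onset of a serious COVID-19 event, and the LOCF and MMRM methods were adopted partly for pandemic-related missingness. None of these helps an excluded patient, who is out of the set before imputation or modelling begins.

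The endpoints concerned are all the clinical measures: neuropathy, quality of life, disability, autonomic symptoms, nutrition, ambulation and functional status. In a single-arm study the change from baseline in those analysed is the whole result. If those removed differ from those kept, the reported change shifts, and no planned table gives the all-treated figure for comparison.

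**Working it through.** **The plan's own figures.** SAP 3.1 assumes an SD of 18% and 16 evaluable patients. The 95% half-width is t(0.975, 15) × 18/√16 = 9.59 (8.82 with the normal quantile), which agrees with the stated value of about 10%. Enrolment is 16/(1 − 0.20) = 20, as stated. These figures concern the primary TTR endpoint and are not in dispute; the same interval formula is used below.

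**Where the cut falls.** Protocol Table 1 schedules dosing on Day 1 and then every 3 weeks to Week 54: 54/3 + 1 = 19 doses. Exclusion starts at 3 COVID-19-missed doses, 3/19 = 15.8% of the schedule. A patient who received the other 16 (16/19 = 84.2%) is dropped at every visit. Eight doses (Day 1 to Week 21) precede Week 24, so all three missed doses can fall after the Month 6 assessments.

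**Weight of one patient.** 1/20 = 5% of the planned sample.

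**Precision.** With k of 20 patients excluded, the 95% half-width in SD units is t(0.975, 19 − k)/√(20 − k). The documents do not give k, so the range is an assumption.

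| k excluded | n analysed | Half-width (SD) | Relative to k = 0 |
|---|---|---|---|
| 0 | 20 | 0.468 | 1.00 |
| 1 | 19 | 0.482 | 1.03 |
| 2 | 18 | 0.497 | 1.06 |
| 3 | 17 | 0.514 | 1.10 |
| 4 | 16 | 0.533 | 1.14 |

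**Possible shift.** If the excluded patients' mean change differs from that of the retained patients by d SD, the Per Protocol mean differs from the all-treated mean by (k/20) × d. The documents give no value or sign for d. Assuming d = 0.5, the shift is 0.025 SD for k = 1 and 0.10 SD for k = 4. Assuming d = 1, it is 0.05 and 0.20 SD. The shift can be favourable or unfavourable, and it is zero when k = 0.

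**What is planned for excluded patients.** SAP 4.1 counts patients in each analysis population. SAP 4.4 lists efficacy data by patient, SAP 4.7.1 lists COVID-19 impact by patient and visit, and SAP 4.7.4 flags assessments made during the pandemic. Weight and laboratory chemistry, which includes the albumin used in mBMI, are summarised on the Safety Analysis Set as safety data. None of these outputs is an all-treated summary of a secondary or exploratory efficacy endpoint.

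**The case against.** The sponsor has a fair case. The change is disclosed twice with a reason. The only hypothesis test is on the primary endpoint, and SAP 3.2 makes all other endpoint summaries descriptive, so type I error is not involved. The protocol's secondary endpoints are changes at 12 months, so a lost Month 6 summary value is not itself the endpoint. With about 20 patients, a reader holding the listings could identify the excluded patients and their values. All of this stands, and it limits the stakes. It does not supply the estimate that protocol 7.2.1 planned: listings hold the raw values but give no all-treated mean change.

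A reader might infer more than the documents support:

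- *That the Safety Analysis Set must be the main set.* SAP Section 5 gives a stated target, the effect in patients with limited pandemic disruption. Which set leads is a disclosed choice; the gap is that the other analysis is absent.
- *That the rule is invalid because it looks at the reason for missed doses and not at exposure.* Patients who stop drug for other reasons, and who "may receive treatment consistent with local standard practice for their disease" while remaining on study, do stay in the Per Protocol set. They are in the Safety Analysis Set too, so adding that analysis changes nothing for them. At most the set is poorly named.
- *That only assessments after the third missed dose should be removed.* Under SAP 3.10.1, doing so would carry Month 6 forward as Month 12 for NIS, Norfolk QoL-DN and R-ODS in exactly these patients.

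**Conclusion.** The point holds as a missing supportive analysis. Protocol 7.2.1 and SAP 2.1, 4.4 and 4.7.2 differ on the set for secondary and exploratory efficacy, and the set now used selects patients on a post-baseline event without an all-treated summary beside it.

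The size is modest and conditional: 5% of the planned sample per exclusion, and intervals about 3% to 14% wider for 1 to 4 exclusions. This assumes 20 treated patients and an unchanged SD. If nobody exceeds the limit, the two sets coincide.

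It would be tempting to say that the exclusion makes results look better, on the view that patients who miss infusions are frailer or progressing faster. The documents do not support a direction; pandemic-related missed doses may equally reflect site closures or travel limits unrelated to disease. Nor do they support a claim of concealment. Primary TTR and safety conclusions do not depend on this point.

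**What to change.** In SAP 2.1, 4.4 and 4.7.2, state that NIS, Norfolk QoL-DN, R-ODS, COMPASS-31, mBMI, PND score, FAP stage and KPS will also be summarised on the Safety Analysis Set, using the same methods, beside the Per Protocol results. Show the number of patients excluded from the Per Protocol set in those tables. Add the line to SAP Section 5.

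The cost is a few sentences of SAP text and a repeat run of existing table programs. It needs no new data, changes no sample size and leaves the sponsor's choice of main set as it is. If no patient is excluded, one statement that the sets are identical is enough.

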2.2. Protocol Deviations

A deviation is considered any departure from the procedures set forth in the protocol. Protocol deviations will be classified into major and minor by medical review. A major deviation includes any deviation that may impact patient safety or efficacy interpretation. Deviations not designated as major will be considered minor. COVID-19 related protocol deviations will be identified.

All protocol deviations, COVID-19 related protocol deviations, and major protocol deviations will be presented in separate data listings.

3. GENERAL STATISTICAL METHODS

3.1. Sample Size Justification

Assuming a normally distributed true TTR percent reduction from baseline of 80% with a standard deviation of 18%, a sample size of 16 patients will yield a 95% confidence interval (CI) with a half-width of approximately 10%. Assuming a 20% premature discontinuation rate, approximately 20 patients will be enrolled in the study.

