7.1. Determination of Sample Size

Assuming a normally distributed true TTR percent reduction from baseline of 80% with a standard deviation of 18%, a sample size of 16 patients will yield a 95% confidence interval with a half-width of approximately 10%. Assuming a 20% premature discontinuation rate, approximately 20 patients will be enrolled in the study.

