7.2.6. Efficacy Analyses

Summary tables and graphical displays of observed values and changes from baseline in serum TTR will be used to assess the durability of suppression over the course of the study. The primary endpoint is the average TTR percent reduction across Month 6 and Month 12. The median TTR percent reduction along with the 2-sided 95% confidence interval will be estimated using the Hodges-Lehmann method. The p-value for the TTR percent reduction will be obtained using the Wilcoxon signed-rank test

Summary statistics of observed values and changes from baseline will be provided for the NIS total score and component scores.

Patient reported quality of life and disease burden will be assessed by summary statistics for the Norfolk QOL-DN and R-ODS. Patient reported autonomic neuropathy symptoms will be assessed by descriptive statistics for the COMPASS 31. Summary statistics will be provided for observed values and changes from baseline.

Descriptive statistics will also be provided for observed values and changes from baseline in nutritional status (mBMI), functional impairment (Karnofsky Performance Status), and ambulation (FAP stage and PND score).

Results of echocardiograms will be summarized.

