4.4.1. Primary Endpoint

The primary endpoint is the average TTR percent reduction from baseline across Month 6 and Month 12.

For all analyses of post-baseline TTR data, only post-baseline TTR assessments collected within 24 days (inclusive) after receiving a complete dose of patisiran (see Section 4.5.1) will be summarized.

The median TTR percent reduction from baseline along with the 2-sided 95% distribution-free CI will be provided. The p-value for the TTR percent reduction from baseline will be obtained using the Wilcoxon signed-rank test.

A summary table will present the observed value, change from baseline, and percent change from baseline in serum TTR by visit. A boxplot will also present the percent change from baseline by visit.

Serum TTR data will be included in a by-patient listing.

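### The half-width of about 10 points in SAP 3.1 does not describe the median CI now planned, which averages 12 to 14 points at n=16 and about 11 at n=20

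*SAP*

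**What the plan says.** Protocol 7.1 justifies the sample size by precision: "a sample size of 16 patients will yield a 95% confidence interval with a half-width of approximately 10" percent. Protocol 7.2.6 names the interval: "The median TTR percent reduction along with the 2-sided 95% confidence interval will be estimated using the Hodges-Lehmann method".

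SAP 3.1 repeats the precision statement: "a sample size of 16 patients will yield a 95% confidence interval (CI) with a half-width of approximately 10" percent. Its premise is "Assuming a normally distributed true TTR percent reduction from baseline of 80% with a standard deviation of 18" percent, and it adds: "Assuming a 20% premature discontinuation rate, approximately 20 patients will be enrolled in the study". It names no interval method.

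SAP 4.4.1 now plans a different interval: "The median TTR percent reduction from baseline along with the 2-sided 95% distribution-free CI will be provided". SAP Section 5 records the change, says that SAS has no one-sample Hodges-Lehmann procedure, and adds: "Based on simulations, the estimated medians and the 2-sided 95% CIs are similar for the two methods". It gives no settings or results for those simulations. The SAP does not say which order statistics will form the limits.

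**The concern.** A distribution-free CI for a median runs from one ordered observation to another. With roughly normal data and a small sample it is usually clearly wider than a t or Hodges-Lehmann interval. If so, the figure in SAP 3.1 belongs to an interval that will no longer be reported, and the similarity claim in Section 5 needs support as far as width is concerned.

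This matters because the half-width is the only quantitative justification for the sample size. If the true reduction is near 80%, excluding zero is almost assured, so the interval is the main statement of how well the reduction is known. The n=16 case is realistic: SAP 4.4.1 uses only TTR samples taken within 24 days of a complete dose, and Protocol 4.3.4 rules out replacing patients.

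**Working it through.** **Inputs (SAP 3.1).** Normal distribution, mean 80, SD 18, 16 evaluable patients, 20% discontinuation, 20 enrolled. Confidence level 95%, two-sided.

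**1. Reproduce the stated figure.** t-interval: 2.131 × 18/√16 = 9.59. Enrolment: 16/0.8 = 20. Both agree with the SAP.

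**2. Coverage of the planned interval.** The interval from the l-th to the u-th ordered value covers the median with probability P(l ≤ B ≤ u−1), where B is Binomial(n, 0.5). At n=16, P(B ≤ 3) = 697/65536 = 0.0106 and P(B ≤ 4) = 2517/65536 = 0.0384.

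- Ranks 5 and 12: 1 − 2 × 0.0384 = 92.3%, so not a 95% interval.
- Ranks 4 and 12, or 5 and 13: 1 − 0.0106 − 0.0384 = 95.1%.
- Ranks 4 and 13: 1 − 2 × 0.0106 = 97.9%.

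**3. Expected half-width.** This is 18 × (E[Z(u)] − E[Z(l)])/2, where E[Z(r)] is the expected r-th standard normal order statistic, found by numerical integration. At n=16, E[Z(13)] = 0.763 and E[Z(12)] = 0.570, with the mirror values at ranks 4 and 5.

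- Ranks 4 and 13: 18 × 0.763 = 13.7.
- Ranks 4 and 12, or 5 and 13: 18 × (0.763 + 0.570)/2 = 12.0.

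Choosing 5–13 rather than 4–12 moves each limit upward by 18 × (0.763 − 0.570) ≈ 3.5 points on average.

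**4. Hodges-Lehmann comparator.** Exact signed-rank limits from the ordered Walsh averages: 30th and 107th of 136 at n=16 (95.6% coverage), 53rd and 158th of 210 at n=20 (95.2%). Mean half-widths come from at least 20,000 simulated trials per n, and the excess is the ratio of simulated means.

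| n | Symmetric ranks (coverage) | Half-width | Narrowest pair reaching 95% (coverage) | Half-width | Hodges-Lehmann | Excess, symmetric / narrowest |
|---|---|---|---|---|---|---|
| 16 | 4, 13 (97.9%) | 13.74 | 4–12 or 5–13 (95.1%) | 12.00 | 9.9 | 39% / 21% |
| 17 | 5, 13 (95.1%) | 11.15 | same | 11.15 | 9.5 | 17% |
| 18 | 5, 14 (96.9%) | 11.97 | same | 11.97 | 9.1 | 32% |
| 19 | 5, 15 (98.1%) | 12.72 | 5–14 or 6–15 (95.9%) | 11.29 | 8.8 | 45% / 29% |
| 20 | 6, 15 (95.9%) | 10.63 | same | 10.63 | 8.5 | 24% |

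No row averages 10 or less. At n=16 the half-width exceeds 10 in 84% of simulated trials with ranks 4 and 13, and in 70% with the narrowest pair. Computed on the same simulated trial, the planned interval is wider than Hodges-Lehmann in 95% (symmetric) or 82% (narrowest) of trials at n=16, and in 85% at n=20.

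**5. Sensitivity to shape (assumption).** The normal model puts 1 − Φ(20/18) ≈ 13% of patients above a 100% reduction, which is impossible. A bounded, skewed alternative is a Beta distribution on 0–100 with mean 80 and SD 18 (parameters about 3.15 and 0.79, median about 85). At n=16 it gives 13.7 for ranks 4–13, 12.8 for 4–12 and 11.2 for 5–13, against 10.1 for Hodges-Lehmann. At n=20 it gives 10.7 against 8.8. The direction is the same. In this case Hodges-Lehmann covers the true median only about 92% (n=16) and 90% (n=20) of the time.

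**The case against.** **SAP 3.1 contains no arithmetic error.** It carries forward the reasoning that fixed the sample size, and Section 5 discloses the change of estimator. This is true, but SAP 3.1 is written as what 16 patients will deliver, and the current plan does not deliver it.

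**The sponsor's simulations are not shown.** They may have used another distribution, SD or sample size, and no threshold for similarity is given. This stands as a limit: the documents cannot show that the simulations were wrong, only that widths differ under the SAP's own planning model. Agreement of the point estimates is not disputed.

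**The 39% and 45% figures compare unequal coverages.** This stands. They set a 97.9% or 98.1% interval against one of about 95%. The fair figure at n=16 is 21%, or about 2 points.

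**Nothing suggests that ranks would be chosen after seeing the data.** This also stands. The change was made for SAS availability, which points to standard procedure output. The unnamed rank rule is a missing detail and not evidence of discretion. The stated precision cannot be corrected without naming it, however.

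**The consequence is small.** The Wilcoxon p-value does not depend on the interval, no decision threshold uses it, and 80 ± 12 to 14 is far from zero. The interval actually obtained will be reported. This is correct, and it keeps the point to a correction of text.

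**Conclusion.** The concern holds. The half-width in SAP 3.1 fits a t or Hodges-Lehmann interval and is out of date for the interval in SAP 4.4.1. Under Normal(80, 18) the expected half-width is 12.0 to 13.7 at n=16, depending on the ranks, and 10.6 at n=20 if all 20 patients are evaluable and ranks 6 and 15 are used. Like for like, the planned interval is 21% wider than Hodges-Lehmann at n=16 and 24% wider at n=20, so the similarity claim in Section 5 does not hold for width under the planning assumptions. These are planning figures and depend on an SD of 18. The assumed bounded, skewed alternative gives the same direction. The test result is unaffected. Keeping the median is defensible, because its interval holds coverage when the data are skewed and Hodges-Lehmann may not.

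**What to change.** 1. In SAP 3.1, name the interval and its rank rule and restate the precision. For example: the distribution-free 95% CI for the median, using symmetric ranks (4th and 13th ordered values at n=16), has an expected half-width of about 14 percentage points with 16 patients and about 11 with 20. If the narrowest pair is preferred, state about 12 at n=16 and say whether ranks 4–12 or 5–13 apply. SAP 4.4.1 should carry the same rank rule.
2. In SAP Section 5, either limit the similarity statement to the point estimates, or give the simulation settings and the interval widths found.

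The cost is a few sentences of SAP text. No more patients and no change of estimator or test are needed. The stated precision becomes less favourable.
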